6.1.5. Skin Irritation Assessment

Draize numerical grades, letter grades and superficial observations will be summarized by visit and assessment location (i.e., back, leg, arm, abdomen and chest). If there are multiple observations of numerical score in an assessment location (e.g., right arm and left arm), maximum score regardless of body side and directionality will be used. Similarly, if there are multiple observations of letter grades or superficial observations, “Y” will be used in

preference to “N” for summarization. For numerical grades, the followings will also be summarized:

- Maximum score by visit, regardless of assessment location;
- Maximum score during the study, regardless of visit and assessment location.

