### 2.2.3. Preclinical Safety Data

In the pivotal 3-month toxicity studies in rats (oral) and minipigs (dermal), the systemic NOAEL were identified as 4 mg/kg/day and 0.0104 mg/cm^2/day (0.0052 mg/cm^2, BID) to 10% BSA, respectively, with systemic exposures of 2x and 1.2x, respectively, the projected maximum human exposure (uCav = 9 pg/mL). The systemic NOAEL exposure identified in the more sensitive nonclinical species (minipig) was 11 pg/mL (Cav, unbound). The local (dermal) NOAEL was identified at the 0.03% concentration (BID) corresponding to 0.0052 mg/cm^2/day (0.0026 mg/cm^2, BID) and represents an 17x multiple to the projected maximum human dermal dose of 0.0003 mg/cm^2/day in the current study. Based on the completed nonclinical studies, local (skin) and systemic (cardiovascular, nervous, and gastrointestinal) target organs/systems were identified. Local reactions (erythema, edema) were observed in minipigs at  $\geq$ 0.00174 mg/cm^2/day (5.8x the highest planned clinical dermal dose, 0.0003 mg/cm^2/day). A potential for skin sensitization by PF-07038124 was identified in a mouse local lymph node assay with a NOEL of 0.015 mg/cm^2/day (50x the highest planned clinical dermal dose, 0.0003 mg/cm^2/day). Cardiovascular effects included increases in heart rate, contractility, and/or blood pressure in rats and/or dogs, and vascular injury/compromise (in mesentery, kidney, adrenal gland, and/or bladder) in rats and/or minipigs. Clinical signs indicative of nervous system effects (eg, ataxia, decreased activity, hunched posture, twitching, and/or tremors) and gastrointestinal effects (emesis, salivation,

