## 4. STUDY DESIGN

### 4.1. Overall Design

This is a Phase 1, randomized, double-blind, vehicle-controlled, parallel cohort study to evaluate the safety, tolerability, skin irritation potential, and PK of PF-07038124 in Japanese healthy adult participants. Both cohorts can be conducted simultaneously.

This study will evaluate the safety, tolerability, skin irritation potential and PK following application of PF-07038124 at 0.01% concentration and vehicle to 2000 cm^2 (Cohort 1; approximately 10% BSA) or 4000 cm^2 (Cohort 2; approximately 20% BSA).

Participants will be randomized to receive PF-07038124 or vehicle in a ratio of 4 PF-07038124: 2 vehicle, per cohort. Each participant will receive multiple doses of

PF-07038124 or vehicle starting on Day 1 topically applied for 10 consecutive days; applied QD in the AM for Cohort 1 and Cohort 2. Participants will not be randomly assigned to cohort. The first group of participants will be enrolled Cohort 1 followed by Cohort 2. All participants will have the study interventions randomly assigned, for the purpose of determining skin irritation potential, as well as PK, safety and tolerability. Dermal reactions at the application site will be assessed clinically using a visual grade that rates the degree of erythema, edema, and other signs of skin irritation.

The total participation time for each participant is approximately 66 days, including the screening period of up to 28 days, the double-blind treatment period of 10 days, and the follow-up period of 28 days from last dose of the study intervention.

Approximately 12 Japanese healthy adult participants are planned to participate in this study.

Participants will be screened within 28 days prior to application of the study intervention to confirm that they meet the selection criteria for the study. Participants will be admitted to the CRU at least 12 hours prior to their planned dose application time (see [Section 6.1.1](#)), and will be required to remain in the CRU until completion of procedures on Day 11 as described in the [SoA](#).

Participants will be followed-up with a phone call per the [SoA](#) following the last dose of study intervention to assess for AEs, SAEs, concomitant treatments, and contraception check. Participants who experience a treatment-related AE will continue to be followed to resolution or stabilization of the event as agreed upon by the investigator and sponsor.

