### **Local Tolerability**

If a participant experiences severity Score 4 (Strong to severe) on the local tolerability assessment ([Section 8.2.5](#)), study treatment will be discontinued permanently, and participant will proceed to Early Termination/Discontinuation visit and follow-up as described in [SoA](#).

If a participant experiences application site reaction of Score 3 (Moderate) on the local tolerability assessment, investigator may temporarily discontinue application of the study intervention for up to 5 consecutive days. If temporary withholding of the study intervention occurs for more than 5 consecutive days, then the participant should be permanently withdrawn from treatment and should follow-up with the site until complete or near complete resolution of the AE. This dosing gap may occur only once for the same participant.

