**Table 4. Skin Irritation Assessment Using Draize Scoring**

Definition	Score
No reaction visible	0
Trace reaction – barely perceptible pinkness	1
Mild reaction – readily visible pinkness	2
Moderate reaction – definite redness	3
Strong to severe reaction – very intense redness	4

Definition of letter grades appended to a numerical grade:

---

J	Burning, stinging, itching
E	Edema – swelling, spongy feeling when palpated
P	Papules – red, solid, pinpoint elevations, granular feeling
V	Vesicles – small elevation containing serous fluid (blister-like), diameter 5 mm or less
B	Bulla reaction – fluid-filled lesion greater than 0.5 cm in diameter
S	Spreading – evidence of the reaction beyond the test site
W	Weeping – result of a vesicular or bulla reaction – serous exudates – clear fluid oozing or covering test area
I	Induration – solid, elevated, hardened, thickening skin reaction
XC	Additional comments appear in Comments section

---

Definition of superficial observations appended to a numerical and/or letter grade:

---

G	Glazing
Y	Peeling
C	Scab, dried film of serous exudates of vesicular or bulla reaction
D	Hyperpigmentation (reddish-brown discoloration of test area)
H	Hypopigmentation (loss of visible pigmentation at test area)
F	Fissuring – grooves in the superficial layers of the skin to glistening
R	Erosion(s)
U	Ulceration(s)
K	Scaling – flaking of skin

---

Photographs of dosing area are taken to document Draize scoring reaction  $\geq 3$  or AE at the treatment application site. These photographs are for illustrative reference only and will be used to document Draize scores  $\geq 3$ .

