### 9.1. Statistical Hypotheses

No statistical hypotheses will be tested in this study.

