## 9.2. Sample Size Determination

A sample size of 12 participants (4 PF-07038124: 2 vehicle per cohort) has been selected empirically to permit adequate characterization of safety, tolerability, skin irritation potential, and PK at each dose level in Japanese healthy participants. Participants who discontinue prior to completion of the study for non-safety related reasons may be replaced, at the discretion of the PI and Sponsor.

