6. ANALYSES AND SUMMARIES

All analyses described below will be conducted by treatment and cohort. In addition, data from vehicle in Cohort 1 and Cohort 2 will be pooled.

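### The Draize number grades redness only, and the SAP plans no whole-study participant incidence for edema, vesicles, erosions and the other non-redness signs

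*SAP*

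**What the plan says.** - **Endpoint.** Protocol 3 and SAP 3.1 make local skin irritation a primary endpoint, in terms of both incidence and severity.
- **What the grade is said to measure.** Protocol 4.1, repeated in SAP 2.2, says application-site reactions are assessed "using a visual grade that rates the degree of erythema, edema, and other signs of skin irritation".
- **What the scale measures.** In Protocol Table 4 and SAP Table 2, score 0 means no visible reaction and scores 1 to 4 rise from barely perceptible pinkness to very intense redness. The other signs come under "Definition of letter grades appended to a numerical grade" or in a further list of superficial observations. None has a degree, and SAP 6.1.5 treats them as Y or N.
- **What is tabulated.** SAP 6.1.5 summarises numbers, letters and superficial observations by visit and body location. It then adds: "For numerical grades, the followings will also be summarized". Two items follow: the maximum score at each visit over all locations, and the maximum over the whole study. Neither has a counterpart for the codes.
- **Where else the number is used.** The Local Tolerability text of Protocol 7.1 is written in terms of the number, for example "If a participant experiences severity Score 4 (Strong to severe) on the local tolerability assessment".

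**The concern.** The headline table for this endpoint will be the maximum numerical score per participant. On the written anchors that is a redness table, although both documents describe something wider. The remaining signs reach the planned tables only in pieces, one visit and one location at a time.

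The signs left out of the collapsed summaries are not remote. Protocol 2.2.3 states: "Local reactions (erythema, edema) were observed in minipigs at" dermal doses above a stated level, so edema is a named nonclinical finding beside erythema. Skin sensitisation is a listed risk in Protocol 2.3.1, with assessment of the application site as part of its mitigation. Under Protocol 8.2.5, edema, papules and vesicles count as present only when they cover at least a quarter of the test area, so a recorded code is not a trivial finding.

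At stake is whether the report can state a participant incidence for each non-redness sign, and whether a participant with such a sign could be presented as having had no reaction.

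**Working it through.** **Inputs**

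- Nature of the study: descriptive. Protocol 9.1: "No statistical hypotheses will be tested in this study". No power or alpha calculation applies.
- Size: Protocol 9.2: "A sample size of 12 participants (4 PF-07038124: 2 vehicle per cohort) has been selected empirically". Check: 2 cohorts × (4 + 2) = 12, which reproduces the stated total.
- Vehicle: SAP 6 says "data from vehicle in Cohort 1 and Cohort 2 will be pooled", so pooled vehicle is 2 + 2 = 4.
- Signs (Protocol Table 4, SAP Table 2): letters J, E, P, V, B, S, W, I = 8; superficial observations G, Y, C, D, H, F, R, U, K = 9; 8 + 9 = 17. XC only points to a comment and is not counted.
- Assessments (Schedule of Activities, skin irritation footnote): predose on Days 1 to 10 plus 24 hours after the Day 10 dose = 11. The first precedes any exposure, leaving 10 post-dose.
- Locations (SAP 6.1.5): back, leg, arm, abdomen, chest = 5.

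**Step 1: how finely the codes are divided**

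Cells per sign per group: 11 × 5 = 55, of which 10 × 5 = 50 are post-dose. These are upper limits, because Protocol 6.1.1.3 does not require every participant to be treated at all five locations.

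**Step 2: what can be recovered from those cells**

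Let n be the group size, c the count in each visit-by-location cell, and N the number of participants who ever had the sign. The table fixes only

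largest c ≤ N ≤ smaller of (n, sum of c).

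Suppose one active participant has vesicles at 2 locations on 3 visits. That fills 2 × 3 = 6 cells, each showing 1 of 4. Then largest c = 1, sum of c = 6 and n = 4, so 1 ≤ N ≤ 4. The same six cells would result if two, three or all four participants shared them.

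| Participants ever affected | Largest cell | Whole-study incidence |
|---|---|---|
| 1 | 1/4 = 25% | 25% |
| 2 | 1/4 = 25% | 50% |
| 3 | 1/4 = 25% | 75% |
| 4 | 1/4 = 25% | 100% |

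The numerical score has no such ambiguity, because its whole-study maximum is counted per participant.

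**Step 3: comparison within the SAP**

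SAP 6.1.3 and 6.1.4 count participants in categories of the maximum vital sign and QTcF values over post-dose measurements. The redness score gets the equivalent. The 17 other signs do not.

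**Step 4: a sign without redness**

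Each code is appended to a number. Scores 1 to 4 require some pinkness or redness on their anchors, and score 0 requires that nothing be visible. Edema on unreddened skin fits neither, and no rule resolves it. A grader who follows the redness anchors records 0 plus the letter. A grader who follows the general labels (trace, mild, moderate, strong to severe) records a higher number. In the first case the maximum-score table counts the participant at 0 unless another assessment scores higher.

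**The case against.** The case against has real force on four points.

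- **Incidence is not absent.** SAP 5.2.1 and 5.2.3 make the default statistic the number and percentage of participants, so each code is counted per participant within each visit and location. SAP 6.1 also says safety endpoints are listed. With 12 participants, a reader could work out who was ever affected. A reader might infer that no output contains this information; that goes too far. What is missing is the tabulated any-location, any-visit figure.
- **Severity is not absent from the whole plan.** Under Protocol 8.2.5 a skin response judged clinically significant is reported as an adverse event, and Protocol 10.3.3 gives every adverse event an intensity. An adverse event at the site also prompts photographs. It would be wrong to infer that blistering on faint redness could appear only as trace or mild. This route depends on investigator judgement, however, and Protocol 8.2.5 exempts other scale findings from it.
- **Counting at 0 is not established.** A grader who sees a blister does see a reaction, and Protocol 8.2.5 speaks loosely of scores for edema, papules and vesicles as well as erythema. The documents support an undefined case, not a known misclassification.
- **Edema is not shown to be as likely as erythema.** Protocol 2.2.3 gives no relative frequencies and places the minipig reactions at 5.8 times the highest planned clinical dermal dose and above. The human data in Protocol 2.2.4.1 mention acne and erythema, all mild, and not edema. No share of the expected signal can be assigned to edema.

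What stands is the absence of a collapsed participant count for signs within a primary endpoint, the mismatch between the description and the scale, and the undefined number for a sign without redness. A small descriptive study makes the listing readable, but a primary-endpoint incidence should not have to be derived by hand.

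**Conclusion.** The point holds as a reporting gap that is cheap to close. It does not affect the sample size or any test, since there is none.

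- The numerical score is a redness score by its anchors, which does not match Protocol 4.1 and SAP 2.2.
- For each of 17 signs, the planned tables can leave whole-study incidence in a four-participant group undetermined between 25% and 100%.
- A participant with a sign but no redness could be presented at score 0, depending on how the grader reads the scale.

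The 25% to 100% range assumes that no cell exceeds 1 of 4 and that at least four cells are filled. It describes the tables read alone, without the listings. The score-0 point assumes grading by the redness anchors.

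**What to change.** In SAP 6.1.5:

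1. For each letter grade and superficial observation (XC excepted), add the number and percentage of participants with the sign at any post-dose assessment and any location, by cohort and treatment and for pooled vehicle.
2. Show participants with any such sign against their maximum numerical score, so that a 0 accompanied by a sign is not reported as no reaction. Keep the rows for individual signs beside it, because the codes range from itching to ulceration.
3. Label the numerical summaries as a redness (erythema) score.

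In the text, reconcile Protocol 4.1 and SAP 2.2 with Protocol Table 4 and SAP Table 2, including which number is recorded when a sign occurs without redness. The sponsor should also reconcile the score-based wording of Protocol 7.1 with these passages. No clinical rule is proposed here.

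The cost is one or two extra tables from data already on the CRF, plus the wording corrections. The downside is a slightly longer skin section and possibly a less favourable irritation figure.

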6.2. Secondary Endpoint(s)

6.2.1. Pharmacokinetic Parameters

PK parameters (AUC_{tau} and C_{max}) will be listed, summarized and plotted for participants in the PK parameter analysis set (as defined in Section 4). Missing values will be handled as detailed in Section 5.3.3. Each PK parameter will be summarized by day and treatment group, and will include the set of summary statistics as specified in the table below:

Table 3. PK Parameters to be Summarized Descriptively

Parameter	Summary Statistics
AUC_{tau} , C_{max}	n, arithmetic mean, median, SD, minimum, maximum, percent coefficient of variation (%CV), geometric mean and geometric %CV

There will be one summary table presenting all PK parameters.

AUC_{tau} and C_{max} will be plotted against treatment group, and will include individual participant values and geometric means for each treatment group. The plots will be paged by day. Geometric means will have a different symbol than individual values. A footnote will be added to the plots to indicate that geometric means are presented.

CCI

CCI

[figure not shown]
CCI

CCI

CCI

[figure not shown]
CCI

[figure not shown]
CCI

CCI

CCI

CCI

6.4. Subset Analyses

No subset analysis will be conducted for this study.

6.5. Baseline and Other Summaries and Analyses

6.5.1. Baseline Summaries

Demographic and baseline characteristics (age, gender, race, ethnicity, weight, height and body mass index) collected prior to the first dose of the study drug will be summarized in accordance with the sponsor reporting standards.

6.5.2. Study Conduct and Participant Disposition

The following participant dispositions will be reported following the sponsor reporting standards:

- A summary of participant discontinuations up to the end of study;
- Summary of participant dispositions analysed for PK and safety;
- Summary of numbers of participant treated by treatment group.

6.5.3. Concomitant Medications and Nondrug Treatments

All concomitant medications as well as nondrug treatments will be provided in the listings.

6.6. Safety Summaries and Analyses

The details of safety analyses are described in the Section [6.1](#).

7. INTERIM ANALYSES

No interim analyses are planned.

Appendix 1. Categorical Classes for ECG and Vital Signs of Potential Clinical Concern

CATEGORIES FOR QTcF

QTcF (ms)	450≤ max. <480	480≤ max.<500	max. ≥500
QTcF (ms) increase from baseline	30≤ max. <60	max. ≥60	

CATEGORIES FOR QT

QT (ms)	max. ≥500		
---------	-----------	--	--

CATEGORIES FOR PR AND QRS

PR (ms)	max. ≥300	
PR (ms) increase from baseline	Baseline >200 and max. ≥25% increase	Baseline ≤200 and max. ≥50% increase
QRS (ms)	max. ≥140	
QRS (ms) increase from baseline	≥50% increase	

CATEGORIES FOR VITAL SIGNS

Systolic BP (mm Hg)	min. <90	
Systolic BP (mm Hg) change from baseline	max. decrease ≥30	max. increase ≥30
Diastolic BP (mm Hg)	min. <50	
Diastolic BP (mm Hg) change from baseline	max. decrease ≥20	max. increase ≥20
Supine pulse rate (bpm)	min. <40	max. >120
Standing pulse rate (bpm)	min. <40	max. >140

Measurements that fulfill these criteria are to be listed in report.
